## 2.10 Planned Interim or Sequential Analysis

No interim analyses will be performed.

## 2.11 Handling of Changes to Study Protocol

Any change which is not only editorial but indicates a change in the statistical analyses planned in the clinical investigation plan (CIP) will be justified and documented at least in the SAP text part if it was decided before database close.

Any change made to the statistical analysis after database close might be described in a new version of the SAP but has to be justified and documented at least in the final clinical investigation report. It has to be specified that these changes occurred after database close and whether they were data-driven or not.

## 3. Technical Aspects and Coding Conventions

All programs will be written using SAS® version 9.4 or higher. There will be an individual SAS® program written for each table, figure and listing. Each analysis program will be validated by a second qualified SAS® programmer to ensure a correct output and a correct presentation of the data. The validation process is documented and filed in the Trial Master File.

All relevant outputs of the SAS® programs will be transferred into RTF documents with DIN A4 format and saved as write-protected PDF documents with a table of content preceding the content of the file. There will be one RTF/PDF document for tables, one for figures and one for listings. The font size should be consistent within each document and reasonable, i.e., there should be as much required information as possible on one page, but the text should be still easy to read.

In headings, titles and listings only the first word will be capitalised. Whenever data are derived, and the derivation method is not obvious from the information given in the header, a footnote should be added to clarify the derivation method. A footnote should also be considered if additional information facilitates the interpretation of the data.

Patient listings will be sorted by site and patient ID unless specified otherwise. Furthermore, derived data will be marked by “#” in patient listings, while missing data will be represented as blank field. If data from a patient is presented by visit, only attended visits will be listed.

### 3.1 Date Coding and Day Numbering

The format for presentation of date variables will be DDMMYY YYYY. The format for presentation of time variables will be hh:mm.

Missing or incomplete dates will not be completed. For additional considerations towards the time allocation of diseases and therapies, refer to Sections 3.2.2 and 3.2.4.

### 3.2 Coding Systems and Conventions

#### 3.2.1 Coding of Adverse Events and Medical History

All medical terms reported as adverse events (AE) or as medical history/concomitant disease are coded according to the Medical Dictionary for Regulatory Activities (MedDRA) version in effect at the time the database is closed for the final analysis. At least the primary system organ class (SOC) as well as the preferred term (PT) should be available for the statistical analysis.

#### 3.2.2 Separation of Medical History from Concomitant Diseases

Separation of past and current medical conditions will be done by comparison of the stop date of the medical condition with the date of study start (Visit 01). Each medical condition will be allocated unambiguously either to medical history or concomitant diseases.

- **Medical history:** If the stop date is before the date of study start (Visit 01), the medical condition will be allocated to medical history. If the stop date is partially given and unambiguously before study start, the medical condition will also be allocated to medical history. Furthermore, if the stop date is missing and the medical condition is not known to be active at start of study participation, findings coded as “Surgical and medical procedures” will also be allocated to medical history.
- **Concomitant diseases:** If the stop date is at or after the date of study start or the medical condition is active at start of study participation, the medical condition will be allocated to concomitant diseases. Furthermore, if the stop date is missing and the medical condition is not known to be active at the start of study participation, findings **not** coded as “Surgical and medical procedures” will be allocated to concomitant diseases.

#### 3.2.3 Coding of Medications

Concomitant medications will be coded using the Anatomical Therapeutic Chemical classification system provided by the WHO Collaborating Centre for Drug Statistics Methodology (WHO-CC). At least the ATC level 2 and 3 should be available for the statistical analysis.

### **3.2.4 Separation of Past from Concomitant Medications**

Separation of past and concomitant medication will not be performed as only concomitant medication will be recorded for this study.

## **4. Analysis Populations and Subgroups**

### **4.1 Analysis Populations**

All patients enrolled in this study will be included in the analysis. No additional analysis sets are defined.

### **4.2 Subgroups**

In order to investigate the impact of certain characteristics on performance, the primary variables will also be examined, provided that there are enough subjects in the respective subgroup, by the following variables:

- Size of ARGOS-IO implant (outer diameter of: 11.3 mm, 11.7 mm or 12.1 mm)
- Gender (male, female)
- Age groups ( $\leq 70$  years at Visit 01,  $> 70$  years at Visit 01)
- Educational level (A-Level, Intermediate, Primary, University, Vocational, Other)

A subgroup analysis for the respective subgroups will only be performed if at least two of the features contain five (5) or more patients.

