7.6 Specification of Subgroups for Analysis

In order to investigate the impact of certain characteristics on performance, the primary endpoints will also be examined, provided that there are enough subjects in the respective subgroup, by the following variables:

- ARGOS-01 patients
- ARGOS-02 patients
- Gender
- Age groups
- Size of ARGOS-IO implant
- Educational level.

The extent of the subgroup analysis will be described in more detail in the SAP.

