## Document History

Version	Date	Author(s)	Description
0.1	18/DEC/2020	[name]	First draft version
0.2	17/MAR/2022	[name]	
Final draft
 
Besides minor editorial changes, the following sections were adapted:
 

• Section 4.2: Subgroups were further specified.

• Section 6.2: Derivation of time since implantation added.

• Section 7.3.3: Time to onset is calculated based on date of implantation.

• Section 7.4.2: Time since implantation added to other patient characteristics.

• Section 7.5: Clarification that device malfunctions will be identified among device deficiencies by a medical expert.

• Section 7.7: AEs of special interest and eye-related AEs will be identified by a medical expert. Analysis by eye was added.

• Section 7.8 Clarifications that external eye photography is not part of this SAP.

• Appendix: Tables for subgroup analysis added.

1.0	04/MAY/2022	[name]	Final version (Only minor editorial changes)

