## 1. Introduction

This statistical analysis plan (SAP) contains a more technical and detailed elaboration of the principal features of the statistical analyses described in the Clinical Investigation Plan ARGOS-03, revision B, dated 11/JAN/2018. The purpose of the SAP is to serve as a guideline for statistical programming and creation of the analysis tables, figures and listings for the clinical investigation plan. The SAP is finalised and signed prior to hard lock of the database and start of the statistical analysis.

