### **4.3 Stratification**

No general stratification will be applied. Only subgroup analyses will be performed for subgroups described in Section 4.2.

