### 7.4.2 Demographics and Other Patient Characteristics

Demographic information and other patient characteristics (i.e. age (year of birth), gender at birth, race, weight, height, BMI and educational level) will be summarized using summary statistics (N, mean, SD, median, minimum, maximum, upper and lower quartile) for continuous variables (i.e. age, weight, height, BMI, time since implantation) or absolute and relative frequencies (n, %) for categorical variables (i.e. gender at birth, race, educational level).

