## 8. Changes in the Planned Analysis

As only one series of measurements of IOP per type of IOP measurement and visit is available, the description of the analysis of the primary endpoint has been adapted to cover this case, in line with the guidance provided by Zhou et al., 2011.

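### SAP 4.2 omits the ARGOS-01/ARGOS-02 split listed in protocol 7.6 without recording why, and its implant-size subgroup partly mixes size with device generation

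*SAP*

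**What the plan says.** Protocol 7.6 (revision C) states that "the primary endpoints will also be examined, provided that there are enough subjects in the respective subgroup". It then names six items: ARGOS-01 patients, ARGOS-02 patients, gender, age groups, implant size and educational level.

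SAP 4.2 opens almost identically but lists only four variables: "Size of ARGOS-IO implant (outer diameter of: 11.3 mm, 11.7 mm or 12.1 mm", then gender, age and education. It adds a threshold: a subgroup analysis runs only if at least two levels each hold five or more patients. SAP 4.3 makes the list exclusive: "Only subgroup analyses will be performed for subgroups described in Section 4.2".

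On departures from the protocol, SAP 2.11 says that any non-editorial change to the planned analysis "will be justified and documented at least in the SAP text part if it was decided before database close". SAP section 8 records one change, which begins "As only one series of measurements of IOP per type of IOP measurement and visit is available". The Document History says only "Section 4.2: Subgroups were further specified". The SAP says it elaborates the analyses "described in the Clinical Investigation Plan ARGOS-03, revision B, dated 11/JAN/2018".

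The patient characteristics in SAP 7.4.2 are "age (year of birth), gender at birth, race, weight, height, BMI and educational level", with time since implantation added. Neither these nor the disposition variables in SAP 6.1 include source study or implant generation.

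**The concern.** The study enrols carriers of two different implants. Protocol 6.1.1 describes the redesign (thickness, haptics, posterior protrusions), and protocol 4.2 reports very different agreement with GAT before and after it. If a few first-generation sensors still behave differently, the pooled limits of agreement may describe neither device. A reader of the planned tables could not tell whether wide limits come from those few sensors or from the second-generation device. The same applies to malfunction rates and device-related event rates.

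The remaining size subgroup makes this worse. Only its 11.3 mm level can contain first-generation implants, so a generation difference could be read as a size effect. The protocol's own size subgroup has the same weakness, but the protocol also listed the split that would expose it.

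**Working it through.** **Inputs**
- Maximum enrolment (protocol 7.2.7): 5 ARGOS-01 and 21 ARGOS-02 patients. 5 + 21 = 26, which reproduces the stated maximum.
- Mean difference, ARGOS-IO against GAT (protocol 4.2): 10.2 mmHg in ARGOS-01 and 2.8 mmHg in ARGOS-02.
- 95% limits of agreement (protocol 4.2): -7.58 to 30.01 and -1.7 to 7.4 mmHg.
- Implant sizes (protocol 6.1.1): ARGOS-01 11.3 mm only; ARGOS-02 11.3, 11.7 and 12.1 mm. Numbers per size are not given.

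**Step 1: SDs of the differences.** Reading the limits as bias ± 1.96 SD, SD = width/3.92.
- ARGOS-01: (30.01 + 7.58)/3.92 = 9.59
- ARGOS-02: (7.4 + 1.7)/3.92 = 2.32

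**Step 2: pooled limits if those values persisted**, with one difference per patient per visit. Let w = n1/(n1 + 21), where n1 is the number of ARGOS-01 patients. For n1 = 5, w = 5/26 = 0.192.
- Mean: 0.192 × 10.2 + 0.808 × 2.8 = 4.2
- Variance = w·SD1² + (1 - w)·SD2² + w(1 - w)·gap² = 17.7 + 4.4 + 8.5 = 30.5, so SD = 5.5
- Limits: 4.2 ± 1.96 × 5.5, about -6.6 to 15.1; width 21.7 against 9.1 for ARGOS-02 alone

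The ARGOS-01 limits have midpoint 11.2, not the stated 10.2. Using both midpoints (11.2 and 2.85) as the biases gives a pooled width of 22.5.

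**Step 3: dependence on ARGOS-01 enrolment**

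| ARGOS-01 patients | 0 | 1 | 2 | 3 | 4 | 5 |
|---|---|---|---|---|---|---|
| Pooled width, mmHg | 9.1 | 13.4 | 16.3 | 18.5 | 20.2 | 21.7 |
| Ratio to ARGOS-02 alone | 1.0 | 1.5 | 1.8 | 2.0 | 2.2 | 2.4 |

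**Step 4: dependence on how far the difference has shrunk** (n1 = 5)

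| Assumption | Width, mmHg | Ratio |
|---|---|---|
| Bias gap removed, ARGOS-01 SD unchanged | 18.4 | 2.0 |
| Bias gap and ARGOS-01 SD both halved | 12.9 | 1.4 |
| Bias gap removed, ARGOS-01 SD halved | 11.6 | 1.3 |
| No difference left | 9.1 | 1.0 |

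**Step 5: size subgroup with no true size effect.** With k ARGOS-02 patients at 11.3 mm, that level shifts by n1 × gap/(n1 + k). The full gap is 10.2 - 2.8 = 7.4. I take k from 15 down to 3 as an assumption.
- n1 = 5, full gap: 5 × 7.4/20 = 1.85 to 5 × 7.4/8 = 4.6 mmHg
- n1 = 5, gap halved: 5 × 3.7/20 = 0.9 to 5 × 3.7/8 = 2.3 mmHg
- n1 = 2, full gap: 2 × 7.4/17 = 0.9 to 2 × 7.4/5 = 3.0 mmHg
- Gap gone: 0

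**Step 6: the SAP's own threshold.** A study split of 5 and 21 meets the rule of two levels with five or more. With 4 or fewer ARGOS-01 patients it fails.

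**The case against.** Five points can be made for the SAP.

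1. **Revision B.** The SAP follows protocol revision B, which was not supplied. If that revision lacked the split, the SAP removed nothing and had nothing to record. This stands as a limit on the charge of an undocumented change. The SAP would then be unaligned with revision C, which still needs reconciling.

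2. **Too few patients.** The protocol made the split conditional on numbers, and the SAP's rule is met only if all five ARGOS-01 patients enrol. That may be the real reason, but the SAP does not give it. ARGOS-01 limits from five patients would indeed be very imprecise: at SD 9.59, a simple 95% interval on each limit is about ± 22 mmHg. This argues for caution with the ARGOS-01 results. It does not argue against an ARGOS-02-only summary, which is feasible however few ARGOS-01 patients enrol.

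3. **The 2.4-fold figure is an upper case.** The ARGOS-01 values come from six patients. Sensors are also checked against GAT at baseline and at least yearly, and adjusted if necessary (protocol 6.1.2 and 6.4.4.7). This is correct, and it is why the range runs down to no effect.

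4. **Partial traceability.** Bland-Altman plots show individual pairs, patient numbers carry over from the source study, ARGOS-01 was single-site, and listings are sorted by site and patient. The 11.7 and 12.1 mm levels are ARGOS-02 only. A determined reader could reconstruct much of this, but the plots are not planned with generation labels, and a listing is not a summary.

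5. **Descriptive study.** There is no hypothesis test, so error rates are untouched. That is true, but description is all this study produces.

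**Conclusion.** The concern holds. The SAP does not match protocol 7.6 as supplied, gives no reason, and leaves no planned summary by device generation for any primary variable. Its size subgroup is partly confounded with generation.

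The pooled limits could be anywhere from no wider to about 2.4 times as wide as those for ARGOS-02 alone. The 11.3 mm level could shift by 0 to 4.6 mmHg without any size effect. These figures are illustrations, not predictions: they rest on the earlier studies' agreement, on limits being bias ± 1.96 SD, on one difference per patient per visit, and on assumed counts per size. Whether the split was dropped, or was absent from revision B, cannot be settled from the documents. Pooling all enrolled patients is the protocol's own plan (section 7.8) and is not in question.

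**What to change.** - Keep the pooled analysis as the main result.
- Restore the ARGOS-01/ARGOS-02 split in SAP 4.2 for limits of agreement, device malfunctions, and device-related AE and SAE rates.
- Exempt this split from the five-patient rule, since one non-participant would switch it off. Always give the ARGOS-02-only summary, and list ARGOS-01 patients individually if they are too few to summarise.
- Restrict the implant-size subgroup to ARGOS-02 implants.
- Add source study to the disposition or patient-characteristics table.
- Record and justify these decisions in SAP section 8, and state which protocol revision the SAP follows. If the database has already closed, SAP 2.11 requires the change to be documented at least in the clinical investigation report, stating whether it was data-driven.

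The cost is wording and a few tables from data already held. By-subgroup tables are already planned for limits of agreement (8.2.1.3) and malfunctions (8.2.2.2), but by-subgroup safety tables would be new. The ARGOS-02-only intervals would be slightly wider, with up to 21 patients rather than 26, and the ARGOS-01 results would be very sparse.

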- Less inflammation: while all patients in the ARGOS-02 trial experienced at least some degree of postsurgical inflammation, in most cases this inflammatory response was similar in intensity and duration to that observed after standard cataract surgery. Most notably, not a single case of hypopyon occurred during the ARGOS-02 trial compared to two cases (33.3%) in the ARGOS-01 trial. There were still five patients (21.7%) who experienced fibrin exudation after surgery

 Implantdata Ophthalmic Products GmbH	Clinical Investigation Plan ARGOS-03	Revision C Page 24 of 67
---------------------------------------------------------------------------------------------------------------------------	-------------------------------------------------------	---------------------------------

(compared to 66.7% in the ARGOS-01 trial), two of which were briefly hospitalized and treated accordingly. All instances of anterior chamber inflammation resolved quickly however and the number of other inflammation related adverse events (corneal edema, cystoid macular edema) was low and comparable to rates reported in literature for cataract surgery alone.

- Less pigment dispersion: pigment dispersion, which may lead to increased intraocular pressure, was reported as adverse event for five out of six patients in the ARGOS-01 and eight out of 22 patients in the ARGOS-02 trial, thus constituting a significant reduction of pigment release to a rate similar to that seen in cataract surgery with sulcus fixed intraocular lenses. Further improvements can be expected, when the level of experience with the redesigned device increases.
- Better performance: concordance between ARGOS-IO measurements and GAT IOP was significantly better than in the ARGOS-01 trial. The mean difference between IOP obtained through ARGOS-IO and GAT was 10.2 mmHg in the ARGOS-01 trial and 2.8 mmHg in the ARGOS-02 trial. The 95% limits of agreement changed from -7.58 mmHg and 30.01 mmHg in the ARGOS-01 trial to -1.7 mmHg and 7.4 mmHg in the ARGOS-02 trial.

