6. DESIGN OF THE CLINICAL OBSERVATIONAL STUDY

6.1 General Aspects

6.1.1 Description of the Type of Clinical Trial

The trial will be conducted as a prospective, open-label, multicenter clinical follow-up trial.

The trial will include the ARGOS-01 patients (max. 5 patients) and the ARGOS-02 patients (max. 21 patients). From the ARGOS-01 study to the ARGOS-02 study, some modifications to the form of the ARGOS-IO implant were made in consequence of the outcomes of the ARGOS-01 study.

The design modifications made included:

- Addition of 4 haptics at the outer edge of the implant
- Reduction in device thickness from a uniform 0.9 mm to 0.5 mm overall, tapering to a 0.1 mm rounded outer edge

 Implantdata Ophthalmic Products GmbH	Clinical Investigation Plan ARGOS-03	Revision C Page 29 of 67
---------------------------------------------------------------------------------------------------------------------------	-------------------------------------------------------	---------------------------------

- Addition of two allantoid protrusions running on either side of the posterior surface from the middle of the ring to the ASIC.

The ARGOS-IO implant used in the ARGOS-01 study had an outer diameter size of 11.3 mm, an inner diameter size of 7 mm and an overall thickness of 0.9 mm. In the ARGOS-02 study three different sizes were used: Ø 11.3 mm, Ø 11.7 mm and Ø 12.1 mm; all with an inner diameter of 7 mm and thickness of 0.5 mm.

All consenting ARGOS-IO patients are eligible for enrolment into the study.

6.1.2 Equipment to be used to assess the clinical trial variables and arrangements for monitoring maintenance and calibration

Sites will use their own ophthalmology diagnostic devices. The requested calibration intervals have to be followed.

Following any ocular procedure and at least once a year the correct function of the ARGOS-IO implant must be confirmed by an experienced and qualified specialist using GAT (the average of 3 ARGOS-IO measurements are compared to one GAT measurement), and adjusted if necessary (please refer to the *Mesograph IFU* for details).

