## 2.9 Sample Size Calculation

Given the exploratory nature of this study, the sample size is not driven by the need for a formal statistical hypothesis test with a certain degree of power and no formal sample size calculation had been performed. Instead, this study is driven by the desire to obtain a clinically meaningful amount of data to evaluate the long-term safety and performance of the ARGOS-IO system in patients who have already been implanted with the study device. Therefore, the maximum sample size is 26. This maximum sample size is composed of maximal 5 available subjects from the ARGOS-01 study and

maximal 21 available subjects from the ARGOS-02 study. It is envisaged to enroll all of these subjects.

The minimal sample size for this study is at the Sponsor's discretion. This is considered to be appropriate since no experimental treatments are planned and all assessments with exception of IOP measurement using the ARGOS-IO device are established standard methods.

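### The 11.3 mm implant-size subgroup mixes two implant generations, so its contrast with 11.7 and 12.1 mm is confounded by generation

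*SAP*

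**What the plan says.** SAP 4.2 examines the primary variables by four characteristics, one of which is "Size of ARGOS-IO implant (outer diameter of: 11.3 mm, 11.7 mm or 12.1 mm". A subgroup analysis is run only if at least two levels hold five or more patients. SAP 4.1 sets a single population: "All patients enrolled in this study will be included in the analysis". SAP 4.3 adds no stratification beyond the 4.2 subgroups. The SAP appendix plans two kinds of subgroup table: limits of agreement (8.2.1.3) and device malfunctions (8.2.2.2).

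Protocol 6.1.1 describes the implants. "The ARGOS-IO implant used in the ARGOS-01 study had an outer diameter size of 11.3 mm", with a thickness of 0.9 mm. The redesign added four haptics and two posterior protrusions and cut the thickness to 0.5 mm. For that device, "In the ARGOS-02 study three different sizes were used: Ø 11.3 mm, Ø 11.7 mm and Ø 12.1 mm".

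Protocol 7.6 lists ARGOS-01 patients and ARGOS-02 patients as subgroups in addition to implant size. SAP 4.2 leaves them out, and SAP section 8 does not record this as a change. The SAP states that it elaborates CIP revision B and the CIP supplied is revision C, so the list in revision B cannot be checked.

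**The concern.** Of the three diameters, only 11.3 mm occurs in both generations. Grouping by diameter alone sends every ARGOS-01 patient to one level and none to the other two. A difference between 11.3 mm and the rest could come from size, from the redesign, or from both, and the planned table cannot separate them.

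The confounder bears on the outcome being tabulated. Protocol 4.2 reports that the first-generation ring gave aberrant readings under radial force and that the redesigned ring did not. It also reports that the mean difference from GAT "was 10.2 mmHg in the ARGOS-01 trial and 2.8 mmHg in the ARGOS-02 trial". The limits of agreement were −7.58 to 30.01 mmHg and −1.7 to 7.4 mmHg respectively. Protocol 7.1.4 gives a gap of more than 5 mmHg from GAT as an example of a malfunction, so an offset tied to generation could also reach the malfunction table.

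SAP 4.2 states that the subgroups are there to investigate how such characteristics affect performance. Without a breakdown by source study, nothing in the planned output would show a reader that the 11.3 mm level is a mixture.

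**Working it through.** **Inputs**

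- ARGOS-01 patients: "maximal 5 available subjects from the ARGOS-01 study" (SAP 2.9). Call the number enrolled *a*, at most 5.
- ARGOS-02 patients: "maximal 21 available subjects from the ARGOS-02 study" (SAP 2.9). The total 5 + 21 = 26 reproduces the stated maximum sample size.
- Mean ARGOS-IO minus GAT in the earlier trials: 10.2 and 2.8 mmHg (Protocol 4.2), a gap of 7.4 mmHg.
- SD of the differences implied by the earlier limits of agreement, as width / (2 × 1.96): ARGOS-01 (30.01 + 7.58) / 3.92 = 9.59 mmHg; ARGOS-02 (7.4 + 1.7) / 3.92 = 2.32 mmHg.
- ARGOS-02 patients with an 11.3 mm implant, *k*: **assumption**. The documents do not give it, so it is varied from 0 to 20.

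**Formulas**

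Assume no true size effect and treat the 11.3 mm level as a mixture with first-generation share p = a / (a + k).

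- Mean = 10.2p + 2.8(1 − p), so the shift against the other sizes is 7.4p.
- Variance = 9.59²p + 2.32²(1 − p) + 7.4²p(1 − p).
- Limits of agreement = mean ± 1.96 SD.

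**Results with a = 5**

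| k | p | Mean (mmHg) | Shift (mmHg) | SD (mmHg) | Limits (mmHg) | Width relative to ARGOS-02 |
|---|---|---|---|---|---|---|
| 0 | 1.00 | 10.20 | 7.40 | 9.59 | −8.6 to 29.0 | 4.13 |
| 7 | 0.42 | 5.88 | 3.08 | 7.40 | −8.6 to 20.4 | 3.19 |
| 11 | 0.31 | 5.11 | 2.31 | 6.65 | −7.9 to 18.1 | 2.86 |
| 16 | 0.24 | 4.56 | 1.76 | 5.99 | −7.2 to 16.3 | 2.58 |
| 20 | 0.20 | 4.28 | 1.48 | 5.61 | −6.7 to 15.3 | 2.42 |

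Worked line for k = 7: p = 5/12; mean = (5 × 10.2 + 7 × 2.8) / 12 = 70.6 / 12 = 5.88; shift = 5.88 − 2.8 = 3.08.

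**Results with a = 1**

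The shift is 7.4 / 21 = 0.35 mmHg at k = 20 and 7.4 / 2 = 3.7 mmHg at k = 1.

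**The five-patient rule**

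- If all five ARGOS-01 patients enrol, they alone bring 11.3 mm to the threshold.
- The rule also requires at least one other size to hold five or more patients, all from ARGOS-02. With 21 such patients, the table runs only if k ≤ 16. The k = 20 line is therefore an outer bound that the rule would suppress.

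**After the fix**

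With only ARGOS-02 patients in the table, a = 0, p = 0 and the shift caused by generation is 0 by construction. At most 21 patients remain across the three sizes.

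**Caveat on the inputs**

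The ARGOS-01 limits have midpoint (30.01 − 7.58) / 2 = 11.2, not the stated mean of 10.2. The ARGOS-01 SD, and the limits built on it, are approximate.

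**The case against.** A reader might infer that the size comparison shows generation and not size. The documents do not support that. The comparison of 11.7 with 12.1 mm lies wholly within the second generation and is untouched. The 11.3 mm level is a mixture whose composition is unknown; confounding means the two influences cannot be separated, not that size plays no part.

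A reader might also infer that 11.3 mm is bound to look worse in ARGOS-03. The 10.2 and 2.8 mmHg come from the earlier trials. Protocol 6.1.2, 6.4.4.7 and 6.5.1 provide for checking the sensor against GAT and adjusting it if necessary: at V01, after any ocular procedure and at least yearly. This acts directly on the mean offset, although it need not remove a difference in spread. For malfunctions, the documents reviewed give no rate by generation.

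A third inference would be that the table could misdirect the choice of implant size. Nothing in the documents links the table to that choice. Protocol 4.2 says the diameter is chosen to fit the individual. Size is therefore tied to eye anatomy, and even an ARGOS-02-only table would not isolate a causal size effect.

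Finally, the study is exploratory, with no hypothesis or test (SAP 2.5, 5.3). The size table is conditional on the five-patient rule, and the overall limits of agreement do not depend on it. Restoring the source-study subgroups of Protocol 7.6 would let a reader see the generation difference.

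All of this limits the size and consequence of the problem. It does not remove it: an exploratory table should still describe the factor it names, and with a source-study table alongside, the 11.3 mm row would still mix two designs.

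**Conclusion.** The point holds as a confounding problem. Followed as written, SAP 4.1 to 4.3 place every enrolled ARGOS-01 implant in the 11.3 mm level, so any contrast of 11.3 mm with 11.7 or 12.1 mm mixes size with generation. That follows from Protocol 6.1.1 and needs no assumption beyond at least one ARGOS-01 patient enrolling.

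The size of the distortion is not known. The mmHg figures are illustrations that rest on earlier-trial means, no true size effect, an assumed *k* and, for the main table, full ARGOS-01 enrolment. They should not be read as the bias expected in ARGOS-03. The point concerns one conditional, exploratory table for each primary performance variable. It deserves correction because the remedy is simple and removes this source of confounding completely.

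**What to change.** In SAP 4.2, restrict the implant-size subgroup, for both limits of agreement and device malfunctions, to ARGOS-02 patients, and apply the five-patient rule to those counts. If ARGOS-01 patients are shown in these tables at all, give them a separate row labelled *11.3 mm, first generation*.

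Also restore the ARGOS-01 and ARGOS-02 subgroups listed in Protocol 7.6. ARGOS-01 can supply at most five patients and so meets the threshold only if all five enrol. SAP 4.2 should therefore say how these two groups are presented if fewer take part.

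The size restriction costs one sentence in the SAP and one filter in the subgroup programs; the restored subgroups add their own rows or tables. The real price is a smaller 11.3 mm level, which may fall below five patients. If fewer than two sizes then reach five, the size table would not be produced.
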